6.1.3 Reporting conventions

All applicable statistical tests will be 2-sided and performed using a 5% significance level. All confidence intervals presented will be 95% and two-sided.

6.1.4 Validation of results

Details of data cleaning and verification, including consistency and range checks, are specified in the Data Management Plan. The analysis of the primary immunological endpoint, including any derivation of outcomes and/or covariates from raw data, will be independently double programmed by two analysts prior to unblinding using a randomly generated dummy variable for treatment allocation; discrepancies in results will be resolved by consensus.

6.1.5 Statistical software

All analyses will be conducted using Stata Version 17.0.

6.1.6 Data management plan

The Data Management Plan will be stored in the Florence eBinder for each trial (Section 12). The version dated May 24th 2022 was used when writing the SAP.

6.1.7 Statistical Master File

Documents relating to the statistical analysis will be store in the Florence eBinder for each trial (Section 15). Documents stored within the Florence eBinder will include this SAP (including evidence of approval/sign-off), statistical reports, and any correspondence related to post-approval SAP amendments.

6.1.8 Reporting

Clinical Study Reports are to be produced for the funder, separately for each trial (Indonesia Trial, BCOV22 Observational Study, and Mongolia Trial). All analyses will be conducted according to the SAP. However, the formatting of figures and tables may be modified, and additional descriptive (but not comparative) statistics provided, to comply with the ICH E3 Guidelines on the Structure and Content of Clinical Study Reports.¹

6.2 TIMING OF ANALYSES

Due to the rapidly evolving nature of the pandemic, analyses will be conducted for each immunological endpoint once the necessary data have been cleaned and locked, which will be as soon as is practicable after all participants have completed their Day-28 visit (for Day-28 endpoints), Month-6 visit (for Month-6 endpoints), or Month-12 visit (for Month-12 endpoints). Necessary data includes those required for the reactogenicity, safety, and breakthrough infection endpoints, and data on intercurrent events, to the same timepoint as for the immunological endpoint that is to be analysed, as these are essential for interpretation. A list of necessary variables is provided in Section 6.3.

For primary endpoint (i) (comparison of binding antibodies at Day-28 between fractional and standard dose groups), it is estimated that the relevant data will be locked within 8 weeks of the final participant completing their Day-28 visit. The statistical analyses will be conducted within 8 weeks of data locking.

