TRIAL POPULATION	Participants will be adults aged 18 years or older who have received	
	two doses of either Sinopharm (BBIBP-CorV®), AstraZeneca	
	(ChAdOx1-S, or Vaxzevria [®]), or Sputnik V (Gam-COVID-Vac [®]) \geq 6	
	months before entering this study. There will be no upper age limit.	
	200 participants will be required in the Sinopharm groups and 100	
	per group in the Astra Zeneca and Sputnik arms, and therefore	
	there will be 800 participants in total. Procedures will be	
	implemented to ensure participants of all ages (aged 18 and above)	
	are included and that there is an even age distribution (<50 and	
	≥50 years) in each group.	
DESCRIPTION OF SITES	Participants will be enrolled at government health centres or	
ENROLLING PARTICIPANTS	hospitals in Ulaanbaatar and provincial sites where Pfizer booster	
	vaccinations are currently being offered to all adults.	
DESCRIPTION OF	The interventions being studied are as follows:	
INTERVENTIONS	Pfizer-BioNTech (BNT162b2, or Comirnaty®) Standard Dose (30µg)	
	Pfizer-BioNTech (BNT162b2, or Comirnaty ®) Fractional Dose (15µg)	
TRIAL DURATION	The total duration of the trial will be 36 months. The initial	
	recruitment period has been completed and took approximately 4	
	months. Each participant will have nine visits over a follow-up period	
	of 24 months following their immunisation visit.	

	To extend the follow-up from 12 months to 24 months after the		
	study vaccine, participants will be invited to reconsent to the study		
	extension following their 12 month visits.		
PARTICIPANT DURATION	Participant duration will be 24 months, and there will be nine visits		
	(six in-person visits and three phone calls). The DSMB will review		
	participant safety regularly during the 24 months of participant		
	involvement. Binding ELISA results (Euroimmun) will be reviewed by		
	the DSMB for all participants who receive a fractional dose and		
	compared with those who received a full dose. They will review all		
	cases that do not meet the seroresponse definition (p38-39). The		
	DSMB will decide if participants who received a fractional dose will		
	be offered a further booster dose.		

GLOSSARY OF ABBREVIATIONS

ABBREVIATION	TERM
AE	Adverse Event
ANOVA	Analysis of Variance
AR	Adverse Reaction
ATAGI	Australian Technical Advisory Group on Immunisation
BRF	Biobank Registration Form (MCRI)
CEPI	Coalition for Epidemic Preparedness Innovations
CMI	Cell mediated immunity

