3.2 Outcomes

3.2.1 Primary outcomes

Immune response

Binding antibody – These will be evaluated using the commercial Euroimmun S1 IgG ELISA on all serum samples collected at 6 timepoints (baseline, 28 days, 6 months, 12 months, 18 months and 24 months). Assays for all subjects will be completed within 4 weeks of sample collection. Assays on the 28 days post-vaccination sample, comparing fractional and standard dose, will be reviewed by the DSMB.

Reactogenicity

Reactogenicity will be measured using the accepted standardised method to evaluate systemic and local side effects following vaccination using a structured questionnaire for days post-vaccination as outlined in Table 1 below.

Table 1. Grading system for evaluation of systemic and local side effects following vaccination (8).

Local Reaction to Injec	table Product ª			
				Potentially Life
	Mild	Moderate	Severe	Threatening
	(Grade 1)	(Grade 2)	(Grade 3)	(Grade 4)
Pain	Does not	Repeated use of	Any use of	ER visit or
	interfere with	nonnarcotic pain	narcotic pain	hospitalization
	activity	reliever >24	reliever or	
		hours or	prevents daily	
		interferes with	activity	
		activity		
Tenderness	Mild	Discomfort with	Significant	ER visit or
	discomfort to	movement	discomfort at rest	hospitalization
	touch			
Erythema/redness ^b	2.5 – 5 cm	5.1 – 10 cm	>10 cm	Necrosis or
				exfoliative
				dermatitis
Swelling ^c	2.5 – 5 cm	5.1 – 10 cm or	>10 cm or	Necrosis
	and does not	interferes with	prevents daily	
	interfere with	activity	activity	
	activity			
Hardness ^c	2.5 – 5 cm	5.1 – 10 cm or	>10 cm or	Necrosis
	and does not	interferes with	prevents daily	
	interfere with	activity	activity	
	activity			
Axillary	Does not	Repeated use of	Any use of	ER visit or
lymphadenopathy	interfere with	nonnarcotic pain	narcotic pain	hospitalization
	activity	reliever >24	reliever or	
		hours or	prevents daily	
		interferes with	activity	
		activity		
Warmth (usually	Absence		Presence	
reported with				
redness)				
Itch	Absence		Presence	

^a For all parameters, grade 0 will be recorded if specific symptoms are absent.

^b The measurement should be recorded as a continuous variable in addition to grading the measured local reaction at the greatest single diameter.

^c Hardness and swelling should be evaluated and graded using the functional scale as well as the actual measurement.

Systemic (General) ^a

				Potentially Life
	Mild	Moderate	Severe	Threatening
	(Grade 1)	(Grade 2)	(Grade 3)	(Grade 4)

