11.4 Interim Analyses

We will conduct an interim analysis of the antibody responses from the 28 days visits to ensure that the responses in the fractional dose groups are adequate. This will be assessed on both individual and group levels by the DSMB. If fractional dose responses are considered inadequate an appropriate rescue strategy will be developed, probably involving a single dose of the vaccine in question at 3 months or as soon as the DSMB has reviewed and made a decision on the results. If the fractional dose is considered inadequate this information will be made public and shared specifically with WHO and other groups working in the field. In addition, an analysis will be undertaken once all data are collected for the 6 months analysis to review the potential need for policy changes. All such analyses will be undertaken by the trial statistician in Melbourne.

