6.4 INTERIM ANALYSIS

There will be no interim analyses, however the final analyses for each endpoint will be conducted as soon as is practicable after all participants have completed their Day-28 visit (for Day-28 endpoints), Month-6 visit (for Month-6 endpoints), or Month-12 visit (for Month-12 endpoints) (see 6.2 Timing of analyses). An interim report will be prepared for CEPI at the end of 2022, which will include the results for the primary endpoints.

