6.8 ADHERENCE AND PROTOCOL DEVIATIONS

Adherence to the intervention is defined as receiving a trial booster vaccination on Day 0. The number and percent of participants who adhered will be presented by study group.

Pre-defined major protocol deviations (with a direct bearing on the primary outcome) are:

- Receiving a 4th dose prior to the Day-28 visit
- Inclusion and randomisation of an ineligible person
- Receiving the wrong trial vaccination
- Day-28 visit occurring outside of the specified time window (between Day 28 and 35 [inclusive], with Day 0 being the day of trial vaccination)

All protocol deviations will be classified as minor or major prior to unblinding. Major protocol deviations are those that are deemed to significantly affect the rights or safety of a trial participant, or the reliability, accuracy, and robustness of the data. The number and percentage of patients with major and minor protocol deviations will be summarised by study group (as per randomisation), with details of type of deviation provided.

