6.10 RESCUE VACCINATION

The protocol specifies that if responses are considered by the DSMB to be inadequate an appropriate rescue strategy will be developed, probably involving a single dose [dosage not specified] of the vaccine in question at 3 months. Rescue vaccination will only be given to participants in the fractional dose groups and will be treated as an intercurrent event using the Treatment Policy strategy, such that the estimand will be a comparison of a standard dose without rescue vaccination vs. a fractional dose with rescue vaccination

^{*}Reasons will be provided.

[^]The number of participants with missing data will be noted (data will be imputed in a sensitivity analysis if missingness is >5%). Missing data arising from lost-to-follow-up or withdrawal will be enumerated, including the level of withdrawal (from intervention, follow-up, or both, and consent to use data up to the time of withdrawal) and reasons (harms-related reasons for withdrawal will be emphasised).

if required for all Month-6 and Month-12 endpoints. Results should be interpreted within the context of the proportion of fractional dose recipients who receive rescue vaccination.

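### At the SAP's time limits, the only scheduled Day-28 dose comparison comes after 3 months for every participant and after Month 6 for about 30% to 65%, with no earlier DSMB output

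*SAP*

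**What the plan says.** Protocol 11.4 plans an analysis of the 28-day antibody responses so that the DSMB can judge, for individuals and for groups, whether the fractional dose is adequate. If it is not, a rescue strategy follows, "probably involving a single dose of the vaccine in question at 3 months or as soon as the DSMB has reviewed" and decided. Protocol 4.2 says that adequacy will be evaluated early in the project. Protocol 3.2.1 sets the laboratory clock: "Assays for all subjects will be completed within 4 weeks of sample collection", with the 28-day assays going to the DSMB. Protocol 10.1.3 gives the DSMB the one-month immunogenicity data by dose.

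SAP 6.1.1 declares that the protocol's interim analysis is now the final analysis of the Day-28 endpoints, run once when all Day-28 data are available. SAP 6.4 states: "There will be no interim analyses". SAP 6.2 estimates that "the relevant data will be locked within 8 weeks of the final participant completing their Day-28 visit", and adds: "The statistical analyses will be conducted within 8 weeks of data locking". SAP 3.3 and 6.10 nevertheless place the probable rescue dose at 3 months, without the protocol's alternative tied to the DSMB's review. SAP 6.10 and Table 13 define the later estimand as the fractional dose with rescue "if required for all Month-6 and Month-12 endpoints", handled by treatment policy.

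**The concern.** The adequacy check exists so that the DSMB can act for people who received a half dose. If the only scheduled comparison of the two doses waits for the last participant, then for lock, then for analysis, it may arrive after the time at which the SAP itself expects rescue to occur.

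There is also a consequence for interpretation. The Month-6 treatment is labelled as including rescue where required. If the group result appears after many Month-6 samples have been drawn, early and late enrollers in the same arm will have had different opportunities for rescue before that sample. The Month-6 contrast then mixes two situations according to calendar time. The supplementary analyses in SAP Table 14 vary only infection and self-initiated fourth doses, so none of them would show this.

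**Working it through.** The documents state no total time from dose to result, so there is no planned figure to reproduce. It has to be built from its parts.

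**Inputs**
- Day-28 visit: "between Day 28 and 35 [inclusive], with Day 0 being the day of trial vaccination" (SAP 6.8).
- Lock: up to 56 days after the final participant's Day-28 visit (SAP 6.2, an estimate).
- Analysis: up to 56 days after lock (SAP 6.2).
- Recruitment: the synopsis says the "recruitment period has been completed and took approximately 4" months; Protocol 1.3 still anticipates 2 months. Both are used.
- One month = 365.25/12 = 30.44 days, so 3 months = 91.3 days and 6 months = 182.6 days.
- Assumption: uniform accrual. The documents give no accrual curve.

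**Last dose to result (upper limit)**
- Visit on Day 28: 28 + 56 + 56 = 140 days; 140/30.44 = 4.6 months.
- Visit on Day 35: 35 + 56 + 56 = 147 days; 147/30.44 = 4.8 months.

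**First dose to result (upper limit, Day-28 visit)**
- 2-month recruitment: 4.6 + 2 = 6.6 months.
- 4-month recruitment: 4.6 + 4 = 8.6 months.

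**Against 3 months.** 140 − 91.3 = 48.7 days, so the result is about 49 days late even for the last participant, and later for everyone else. For the last participant to have it by 3 months, lock and analysis together could take at most 91.3 − 28 = 63.3 days, or 9.0 weeks.

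**With no lock or analysis time at all**
- 4-month recruitment: the last Day-28 visit falls 4 + 28/30.44 = 4.92 months after the first dose. The share not yet past 3 months is 63.3/121.75 = 52%, so about 48% are already past it.
- 2-month recruitment: the interval is 2.92 months and nobody is past 3 months.

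**Against Month 6.** At the limits, the result precedes the last participant's Month 6 by 182.6 − 140 = 42.6 days. The share of participants with the result before Month 6 is 42.6 divided by the recruitment length in days.

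| Recruitment | Result before Month 6 | Past Month 6 |
|---|---|---|
| 4 months (121.75 days) | 42.6/121.75 = 35% | 65% |
| 2 months (60.9 days) | 42.6/60.9 = 70% | 30% |

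With the last visit on Day 35 the margin is 35.6 days, and the shares past Month 6 become about 71% and 41%. If 28 days are assumed to pass between result and Month-6 sample, 14.6 days remain, and only 12% (4 months) or 24% (2 months) have the result in time.

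**Against Month 12.** 365.25 − 140 = 225 days remain for the last participant. Even the first participant, at 8.6 months, has the result before Month 12.

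**Individual assay route.** 28 + 28 = 56 to 35 + 28 = 63 days, or 1.8 to 2.1 months after the dose. That is before 3 months.

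**The case against.** The strongest reply is that nothing here is impossible.

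- The 8-week periods are ceilings and SAP 6.2 aims for analysis as soon as practicable. This stands: 4.6, 6.6 and 8.6 months are upper limits, not delivery dates.
- The protocol lets rescue follow the DSMB's decision whenever that comes. This stands for the protocol, but SAP 3.3 and 6.10 leave the clause out. The SAP's page header cites version 4 of the Mongolian protocol, while the protocol in hand includes a 24-month extension that the SAP does not cover. A version difference may therefore explain the omission, but the texts still disagree.
- The DSMB is to review individuals as well as groups, using assays due by about Day 56 to 63, and the synopsis sends it every case that fails the seroresponse definition. The SAP does not forbid this, and the DSMB charter is not among the documents. This also stands, with one limit: the SAP schedules no report to serve that review. The only early report it names is for the funder, at the end of 2022.
- With 4-month recruitment, waiting for all Day-28 visits causes much of the delay before any lock or analysis time is counted. That is right, and it means faster analysis alone would not remove the conflict.
- Dummy Table S1 is a template whose columns are not the Mongolian groups, so its single rescue row, before Month 6, is weak evidence of intent.

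A reader might infer that the timetable cannot inform rescue at all, that participants with a poor response would necessarily wait past 3 months, or that the Month-6 estimand is undefined. The documents support none of these. The individual route could deliver results before 3 months. Some participants would have the group result before Month 6 even at the limits. A treatment-policy estimand is defined whatever share is rescued, and SAP 6.10 already asks for results to be read in light of that share.

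**Conclusion.** The concern holds as a conflict between documents with a practical consequence. If both 8-week limits are used, the group-level comparison arrives after 3 months for every participant, whichever recruitment figure applies. It arrives after Month 6 for about 30% (2-month recruitment) to 65% (4-month) under uniform accrual, with the last visit on Day 28. Rescue exposure at Month 6 would then vary with enrolment date and be absent for many, although the estimand stays defined. Month 12 and the primary non-inferiority test are not affected.

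The 3-month result needs lock and analysis together to exceed about 9 weeks before it applies to everyone. With 4-month recruitment it applies to about half of participants even with no lag. The Month-6 shares depend on the accrual assumption and on which recruitment figure is used. This should be corrected, but it does not undermine the primary analysis.

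**What to change.** Reconcile SAP 3.3, 6.1.1, 6.2, 6.4 and 6.10 with Protocol 3.2.1, 10.1.3 and 11.4, including the timing clause that the SAP omits.

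1. **DSMB report.** Add to SAP 6.2 and 6.4 a descriptive Day-28 ELISA and seroresponse report by arm for the DSMB, produced on the protocol's 4-week assay clock. State that it is separate from the final non-inferiority test, which stays as planned.
2. **Who prepares it.** Name someone outside the blinded analysis team, such as the independent statistician who supplied the randomisation schedule. Protocol 11.4 assigns these analyses to the trial statistician and SAP 3.5 has analysts develop code on dummy allocations, so both need matching wording.
3. **Month-6 wording.** State in SAP 6.10 and Table 13 that rescue before the Month-6 sample may depend on enrolment date.
4. **Reporting.** Add a row to Dummy Table S1 for rescue after the Month-6 visit.

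The cost is one descriptive table set, a few sentences of SAP text, and controlled handling of allocations before lock. Whether, when and how rescue is given stays with the DSMB.

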6.3 LIST OF NECESSARY VARIABLES

Below is a list of necessary variables that need to be cleaned and locked for the analysis of each immunological endpoint to be triggered, in addition to the immunological parameter itself:

Third dose allocation (arm)

- Trial vaccine
- Primary series vaccine strata
- Age group strata
- Dates of first and second doses
- Date of trial vaccine (Day 0)
- Date of blood-draw/study visit
- Reactogenicity for all solicited reactions on 7 days, including grading (Day-28 timepoint only)
- SARS-CoV-2 infection, including clinical spectrum, and date of positive test (to relevant timepoint)
- Receipt of 4th dose (yes/no, and date) (to relevant timepoint)
- Adverse events (severity, causality, SOC, seriousness, expectedness, and outcome) (to relevant timepoint)
- Baseline value of the immunological parameter to be analysed

6.4 INTERIM ANALYSIS

There will be no interim analyses, however the final analyses for each endpoint will be conducted as soon as is practicable after all participants have completed their Day-28 visit (for Day-28 endpoints), Month-6 visit (for Month-6 endpoints), or Month-12 visit (for Month-12 endpoints) (see 6.2 Timing of analyses). An interim report will be prepared for CEPI at the end of 2022, which will include the results for the primary endpoints.

6.5 MULTIPLICITY ADJUSTMENT

For the primary objective, which tests for non-inferiority of a fractional dose compared to the standard dose, for each trial vaccine, no adjustment for multiplicity is necessary as these vaccines are distinct such that a global null hypothesis is not relevant.²

Secondary outcome results will be interpreted precisely (including the timepoint and the specific outcome) so that the per-comparison-wise error rate is not increased and adjustment for multiplicity is not required.³

6.6 PARTICIPANT DISPOSITION

A CONSORT flow diagram will be used to summarise the study population from screening to analysis, including the number of people who were:

- Screened for eligibility
 - o and were eligible at screening
 - and were ineligible at screening (screen failures)*
- Eligible at screening but not randomised*
- Ineligible at screening but randomised (protocol violation)*
- Eligible and randomised

[Subsequent numbers will be given by study group]

- · Allocated to each study group
 - o and received the allocated vaccine
 - and did not receive the allocated vaccine*
- Included in the Reactogenicity and Safety Population (according to vaccine received not allocated)^{*}
- Included in the Primary Day-28 Immunology Population^{*}
- Included in the Secondary Day-28 Immunology Population^{*}
- Included in the Month-6 Immunology Population[^]

Included in the Month-12 Immunology Population^{*}

6.7 PATIENT CHARACTERISTICS AND BASELINE COMPARISONS

Baseline and demographic characteristics, including stratifying variables (primary series and age group) will be described by study group; see Dummy Table 2. Categorical variables will be described with the number in each category and corresponding percentage of the whole study group. Normally distributed continuous variables will be described by the mean, standard deviation, and minimum and maximum values. Nonnormally distributed continuous variables will be described by the median, 25th and 75th percentiles, and minimum and maximum values. Statistical tests for differences between study groups at baseline will not be performed.

6.8 ADHERENCE AND PROTOCOL DEVIATIONS

Adherence to the intervention is defined as receiving a trial booster vaccination on Day 0. The number and percent of participants who adhered will be presented by study group.

Pre-defined major protocol deviations (with a direct bearing on the primary outcome) are:

- Receiving a 4th dose prior to the Day-28 visit
- Inclusion and randomisation of an ineligible person
- Receiving the wrong trial vaccination
- Day-28 visit occurring outside of the specified time window (between Day 28 and 35 [inclusive], with Day 0 being the day of trial vaccination)

All protocol deviations will be classified as minor or major prior to unblinding. Major protocol deviations are those that are deemed to significantly affect the rights or safety of a trial participant, or the reliability, accuracy, and robustness of the data. The number and percentage of patients with major and minor protocol deviations will be summarised by study group (as per randomisation), with details of type of deviation provided.

